4. GENDER/MINORITY MIX

We expect approximately 45% of the patients to be women. Because several participating centers will be VA Medical Centers, the majority of enrolled patients will be men. We will make every effort to recruit a diverse group of subjects, but there are no race or ethnic-based questions to this protocol.

5. RISK ANALYSIS

5.1. Anticipated Risks

There are no risks incurred with the study that are beyond those associated with the clinically warranted procedure (colonoscopy with EMR, see background section). In theory there is a minimal risk associated with an increased time needed to apply clips for closure of the mucosal defect. Dependent on the size of the lesion endoscopic clipping may take 5 to 10 additional minutes. Considering that an EMR of large polyps often takes more than 60 minutes, the additional relative increase in procedure time would be low. Furthermore, there has been no study to show that a small proportional increase in procedure time is associated with an increased risk. Should there be any concern regarding the safety of the patient related to prolonged procedure time when applying clips, the procedure will be aborted.

Risk/Benefit analysis. It is unknown whether the patient will benefit from the proposed study.

The planned interventions are variations of standard of care and the study compares different approaches representing a comparative effectiveness study. While the risk of added time in the clip group may be minimal (if present at all), it is plausible that clip application will decrease bleeding risk and may improve polyp resection. If so, fewer follow-up procedures (either colonoscopy or surgery) would be needed, which might lower the future overall risk. Whether clip application is truly a helpful modification of the EMR resection practice is not known, hence the study.

As for the comparison of cautery settings (Endocut vs. lower power coagulation), it is unclear, which mode is associated with fewer complications. It is the purpose of this study to explore whether one choice of cautery setting may be associated with a lower risk. This understanding may ultimately contribute to an improved polyp resection practice.

5.2. Adverse Event Recording and Reporting

5.2.1. Adverse event definitions

Adverse effect: Any untoward medical occurrence in a clinical study of an investigational device; regardless of the causal relationship of the problem with the investigational device.

Associated with the investigational device: There is a reasonable possibility that the adverse effect may have been caused by the investigational device.

Disability: A substantial disruption of a person's ability to conduct normal life functions.

Life-threatening adverse effect: Any adverse effect that places the subject, in the view of the investigator-sponsor, at immediate risk of death from the effect as it occurred (i.e., does not include an adverse effect that, had it actually occurred in a more severe form, might have caused death).

Serious adverse effect: Any adverse effect that results in any of the following outcomes: death, a life-threatening adverse effect, inpatient hospitalization or prolongation of existing hospitalization, a persistent or significant disability/incapacity, or a congenital anomaly/birth defect.

Hospitalization shall include any initial admission (even if less than 24 hours) to a healthcare facility as a result of a precipitating clinical adverse effect; to include transfer within the hospital to an intensive care unit. Hospitalization or prolongation of hospitalization in the absence of a precipitating, clinical adverse effect (e.g., for a preexisting condition not associated with a new adverse effect or with a worsening of the preexisting condition; admission for a protocol-specified procedure) is not, in itself, a serious adverse effect.

Unexpected adverse effect: Any adverse effect, the frequency, specificity or severity of which is not consistent with the risk information described in the clinical study protocol.

Unanticipated adverse device effect: Any serious adverse effect on health or safety or any life-threatening problem or death caused by, or associated with, a device, if that effect, problem, or death was not previously identified in nature, severity, or degree of incidence in the investigational plan, or any other unanticipated serious problem associated with a device that relates to the rights, safety, or welfare of subjects.

5.2.2 Eliciting adverse effect information

Clinical study subjects will be routinely questioned about adverse effects at study visits. See section "Follow-up Procedures".

5.2.3 Recording and assessment of adverse effects

All observed or volunteered adverse effects (serious or non-serious) and abnormal test findings, regardless of treatment group, if applicable, or suspected causal relationship to the investigational device will be recorded in the subjects' case histories. For all adverse effects, sufficient information will be pursued and/or obtained so as to permit 1) an adequate determination of the outcome of the effect (i.e., whether the effect should be classified as a *serious adverse effect*) and; 2) an assessment of the causal relationship between the adverse effect and the investigational device.

Adverse effects or abnormal test findings felt to be associated with the investigational device or, if applicable, other study treatment or diagnostic product(s) will be followed until the effect (or its sequela) or the abnormal test finding resolves or stabilizes at a level acceptable to the investigator-sponsor.

5.2.3.1 Abnormal test findings:

An abnormal test finding will be classified as an *adverse effect* if one or more of the following criteria are met:

- The test finding is accompanied by clinical symptoms.

- The test finding necessitates additional diagnostic evaluation(s) or medical/surgical intervention; including significant additional concomitant drug or other therapy.
- The test finding leads to a change in discontinuation of subject participation in the clinical study.
- The test finding is considered an adverse effect by the investigator-sponsor.

5.2.3.2. Causality and severity assessment:

The investigator-sponsor will promptly review documented adverse effects and abnormal test findings to determine 1) if the abnormal test finding should be classified as an adverse effect; 2) if there is a reasonable possibility that the adverse effect was caused by the investigational device; and 3) if the adverse effect meets the criteria for a *serious adverse effect*.

If the investigator-sponsor's final determination of causality is "unknown and of questionable relationship to the investigational device or, if applicable, other study treatment or diagnostic product(s)", the adverse effect will be classified as *associated with the use of the investigational device* for reporting purposes. If the investigator-sponsor's final determination of causality is unknown but not related to the investigational device, this determination and the rationale for the determination will be documented in the respective subject's case history.

5.2.4. Reporting of adverse effects to the responsible IRB

In accordance with applicable IRB policies, the investigator-sponsor will report, to the IRB, any observed or volunteered adverse effect that is determined to meet all of the following criteria: 1) *associated with the investigational device or, if applicable, other study treatment or diagnostic product(s)*; 2) *a serious adverse effect*; and 3) *an unexpected adverse effect*. Adverse event reports will be submitted to the IRB in accordance with the respective IRB procedures.

Applicable adverse effects will be reported to the IRB as soon as possible and, in no event, later than 10 calendar days following the investigator-sponsor's receipt of the respective information. Adverse effects which are 1) *associated with the investigational device*; 2) *fatal or life-threatening*; and 3) *unexpected* will be reported to the IRB within 24 hours of the investigator-sponsor's receipt of the respective information.

Follow-up information to reported adverse effects will be submitted to the IRB as soon as the relevant information is available. If the results of the sponsor-investigator's follow-up investigation show that an adverse effect that was initially determined to not require reporting to the IRB does, in fact, meet the requirements for reporting; the investigator-sponsor will report the adverse effect to the IRB as soon as possible, but in no event later than 10 calendar days, after the determination was made.

5.3. Withdrawal of subjects due to adverse effects

The study intervention will only applied once after a study polyp resection. The clip will typically fall off within 1-2 weeks and excreted with a bowel movement, which is usually not noticed by the patient. A continued exposure to the study intervention is therefore not given.

Should the patient have the wish to withdraw from the study, no he/she will no longer be followed as part of the study.

6. FDA RISK DETERMINATION

The study will use the Resolution clip, which was approved by the FDA primarily for hemostasis (treatment of intestinal bleeding) and closure of perforations (FDA-K122660; December 3, 2012). Closure of a mucosal defect after polyp resection was not an FDA approved indication at the time of study commencement. The FDA reviewed the study protocol, and determined in its response from the clip to be a non-significant risk device (March 5, 2014; Q131671, (Appendix 3)).

The FDA has recently revisited indications for the Resolution clip and determined (based on the retrospective study by Liaquat¹⁷, table 1) that the clip can be used for “Prophylactic clipping to reduce the risk of delayed bleeding post lesion resection” (Appendix 501K, December 1, 2014). Clip closure (study intervention) is therefore now an FDA approved clip application.

7. CONSENT PROCESS

Standard Consent Process

Potential study participants include patients between 18 and 89 years of age who are scheduled for a colonoscopy and for a resection of a large ($\geq 20\text{mm}$ polyp).

According to the requirements of local IRBs, patients will be informed about the study within appropriate time prior to the study.

According to the local requirements some site investigators will send out a letter to potential participants to inform about the study and include a consent form for review (i.e. VA White River junction and Dartmouth-Hitchcock Medical Center). The letter will also contain contact information for questions to allow the patient to call the study investigator or coordinator directly with questions. The letter will also allow the study investigator/coordinator to contact a potential study participant, after they have received the letter, to discuss their interest in participating. Upon arrival for the scheduled colonoscopy patient's record will be reviewed to determine eligibility. Patients will be informed about the nature of the study and the possibility to enroll in the study. The individual, who obtains the consent, will answer possible questions. The consent will be obtained at the same time as the consent for the colonoscopy prior to the procedure.

Alternative Consent Process

In addition to the standard of consenting we request the study allows an alteration of the regular consent process for patients who are found to have a large ($\geq 20\text{mm}$) non-pedunculated polyp at the time of the colonoscopy.

Any patient who presents for a colonoscopy between the ages of 18 and 89 and who does not meet exclusion criteria, an information sheet about potential study participation will be mailed prior to the scheduled colonoscopy, and also given to the patient upon arrival for the scheduled colonoscopy. This information sheet contains information about possible enrollment into a study, if a large $\geq 20\text{mm}$ polyp is found along with assurance that any approach follows standard of care. If the patient does not agree to be considered for the study, he/she can actively opt out by initialing the appropriate box at the information sheet. In that case a polyp will be resected per endoscopist preference.

If the patient does not opt out and a large polyp is found the standardized resection protocol (as detailed above) will be followed and patients will be randomized accordingly. Following the procedure the patient/accompanying person will be informed about the findings, the polyp resection, and the possibility to participate in the study. The patient will be given a consent form to be read at home and contacted following the procedure (but more than 24 hours) to discuss

the consent form. If the patient wishes to participate he/she may then sign the consent form and send it to the study coordinator or bring it at his/her next appointment. Only then and if the patient signs the consent, he/she will be enrolled into the study. Telephone consent will be documented in the patient's records.

We believe that such approach is responsible for two reasons – first the studied resection methods are all considered standard of care, and it is unclear which one is superior; and second, large polyps ($\geq 20\text{mm}$) are very uncommon (approximately 1-2%), and it would be impractical to consent each person who presents for a colonoscopy prior to the procedure just in case a large polyp is found.

Privacy and Confidentiality

All patient information will be kept confidential and only information relevant to the study will be recorded. Each site, each patient, and each endoscopist will be given a unique identification number and all study data will be recorded on a case report form. Each form will be kept as a hard copy and stored in a locked cabinet. Collected data will be transferred from each form to an electronic database for further analysis. Data that will be sent to the coordinating center will only contain event dates (including procedure dates, surgery dates, and patient contact dates) as the only patient identifier. Only dates and no other identifiers will leave each site. Patients will be asked in the consent form, whether they agree to share dates with the coordinating center. Each site research team will have access to their data, however, only the primary investigator and the team at the coordinating center will have access to the entire data set. For de-identification purposes each site will keep a separate de-identification log (matching name with assigned ID). This list will be kept separately at each center in a locked cabinet.

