3.1.4. Clipping and complication risk

It is apparent that resection of a large polyp leaves behind a large mucosal defect. The mucosal ulcer that forms after polyp resection can take several weeks to heal. Bleeding complication typically occur within 7 to 10 days, requiring often admission, a repeat

colonoscopy to stop bleeding, and possible blood transfusions. To reduce the risk of bleeding it has been proposed to close the mucosal defect after polyp resection.

To date, no randomized trial has examined whether clip application affects complications after large polyp resection. One recent study did not show a benefit²¹. Bleeding occurred in 2% in either group. However, the study included patients with smaller polyps (mean size 8mm) with a low expected bleeding risk. A recent retrospective study by Liaquat et al. showed that clip closure was associated with a significantly reduced risk of delayed bleeding (2% vs. 10%), and a reduced risk of overall complications (4% vs. 12%), when compared to historical controls²². Main limitations of the study include unmeasured factors that may have affected the outcome and performance of all resections by one expert colonoscopist. However, a third very recent retrospective study by Qumseya et al. reviewed their experience with 525 large colon polyp resection and did not find that clip closure was associated with delayed bleeding complications¹⁶.

In clinical practice use of clips after polyp resection is largely dependent on endoscopist preference and availability. In preparation for this study informal evaluation of polyp resection practice showed that some endoscopists use clips, and others do not. The unclear benefit with using clips, the required technical skills to achieve clip closure of the mucosal defect, and the additional cost may prevent some from using clips routinely.

Whether clip application prevents bleeding and other complications following resection of large polyps and may reduce overall cost of care remains an important clinical question: there is no established superior method, the issue arises daily, the potential impact on clinical practice from a definitive trial would be significant, both to establish an optimal approach and in terms of patient benefits.

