3.2.3. Study screening procedures

To determine patient eligibility:

- Review of the patient's personal medical history
- Review of medical records to verify patient inclusion and exclusion criteria (age, comorbid conditions, anticoagulation).

To determine polyp eligibility:

- Examining eligibility of a potential study polyp during the colonoscopy with respect to polyp inclusion and exclusion criteria (size, morphology).

Potential study participants include patients with a ≥ 20 mm non-pedunculated colorectal polyp (= study polyp).

Identification of study participants:

- Patients with a known ≥ 20 mm polyp detected at a prior colonoscopy and referred for resection of this polyp.
Patient characteristics (age), comorbidities (see exclusion criteria), and medications (exclusion of coagulopathy) will be reviewed prior to the procedure. The patient will be informed about potential study participation. If the patient agrees to participate and after informed consent is provided, the colonoscopy will be performed. Whether a polyp will meet inclusion criteria (size and morphology) will be determined during the colonoscopy. If the patient does not have a polyp that meets the inclusion criteria, the patient will not be included and considered a screen failure.

An alternative subject identification may be applied at some centers with fewer referrals for polyp resection. Any patient who is scheduled for an elective colonoscopy will be provided with an information sheet that allows him/her to opt out to be considered for study enrollment. If the patient does not opt out and if an eligible study polyp is detected during the colonoscopy, the patient may be randomized to one of the four protocol arms (only if patient and polyp inclusion/exclusion criteria are met). The Polyp resection will be performed as determined by randomization. Following the procedure the patient will be informed about the

randomized approach to polyp resection and informed about potential participation in the study. Only after the patient provides informed consent, he/she will be included in the study (see Alternative Consent Process).

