3.2.5. Allocation to treatment (Randomization process)

Randomized will occur at the time of colonoscopy when a polyp has been identified as a study polyp using computer generated randomization. Patients will be randomized following a 2 x 2 factorial design to: (i) Endocut vs. low power coagulation after inspection of the polyp and decision to resect the polyp, and (i) clipping vs. no clipping of the mucosal defect after resection.

Patients will hence be randomized to one of four groups:

- A) Endocut and clipping,
- B) Endocut and no clipping,
- C) Low power coagulation and clipping, and
- D) Low power coagulation and no clipping.

Should a patient have more than one study polyp, all polyps will be resected in the same way (per patient randomization). The primary comparison will be between clip and no clip application. The comparison between cautery currents is secondary and exploratory.

Breaking the blind: The study is not blinded.

Treatment adherence/study compliance: The primary intervention (one-time clip placement) does not require adherence to the intervention. Participants will therefore not be excluded because of non-compliance.

The major outcome of interest will be assessed after 30 days following the intervention by a phone call. We expect that such short interval will allow an almost complete follow-up.

Secondary outcomes of interests include polyp recurrence during longer-term follow-up. We will collect data on all follow-up procedures that are performed as per standard of care (not as a study intervention).

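### On the alternative consent route patients decide about joining after randomization and treatment, with no deadline, so randomized non-signers leave the intention-to-treat set without being counted by arm

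*Combined protocol and SAP*

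**What the plan says.** Section 3.2.3 introduces a second way into the trial: "An alternative subject identification may be applied at some centers with fewer referrals for polyp resection". A patient who has not opted out, and in whom an eligible polyp is found, may be randomized to one of the four arms and treated accordingly. Only afterwards is the patient told about the "randomized approach to polyp resection and informed about potential participation in the study". The section then states: "Only after the patient provides informed consent, he/she will be included in the study".

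Section 7 (Alternative Consent Process) gives the same order. The patient takes a form home and is "contacted following the procedure (but more than 24 hours) to discuss" it. The form may be posted or brought to the next appointment. "Only then and if the patient signs the consent, he/she will be enrolled into the study". The paragraph adds: "Telephone consent will be documented in the patient's records". It sets a minimum delay before contact but no latest date for the decision.

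Other relevant provisions:
- Section 3.2.5: "The study is not blinded".
- Section 3.1.4: "Bleeding complication typically occur within 7 to 10 days". Section 3.2.9.2 counts delayed bleeding from when the patient leaves the endoscopy unit, up to 30 days.
- Section 3.2.10.1 compares the arms as randomized and calls this intention-to-treat.
- Section 3.3.2 (Research Materials) limits data collection to people who participate.
- Section 3.2.2 keeps a log of referred patients who were not consented, with reason, age and gender. Arm is not listed.

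**The concern.** On this route the decision to join comes after allocation, after treatment and possibly after the outcome. If willingness to sign depends on arm and outcome together, the comparison among signers is biased even though the allocation was random. For example, a patient who has bled and knows that the defect was left open might be more, or less, willing to sign than a patient who bled after clipping. The direction cannot be predicted.

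The plan would also not reveal the problem. Sections 3.2.10.1 to 3.2.10.3 contain no analysis by consent route and no report of how many randomized patients in each arm did not sign. Section 3.2.10.1 says the primary and secondary endpoints are meant to support clip labeling, so an unreported exclusion after randomization matters.

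**Working it through.** **The plan's own figure.** Section 3.2.10.4 assumes 8% vs 3%, two-sided alpha 0.05 and 80% power.
- Without continuity correction: n = [1.96·√(2·0.055·0.945) + 0.842·√(0.08·0.92 + 0.03·0.97)]² / 0.05², which gives 326 per arm.
- With the correction, (n/4)·[1 + √(1 + 4/(n·0.05))]² gives 365 per arm, or 730 in total, as stated.
- 730/0.8 = 913 (stated as about 920) and 920/0.9 = 1,022 (stated as 1,020).

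The sample size is therefore not in dispute. That section does treat consent as preceding the intervention and expects no dropouts; neither fits the alternative route.

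**Sequence on this route.** Randomization and resection; discharge, when the endpoint window opens; contact after more than 24 hours; decision at any later time. Bleeds typically occur within 7 to 10 days, so a bleed can precede the decision. The next colonoscopy that Section 3.2.7 aims to schedule is at 3 to 4 months, after the 30-day window has closed.

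**Model for the size of the bias.** Let f be the share of patients on this route, p the true bleeding rate, d_b the refusal rate among bleeders and d_n the refusal rate among non-bleeders. The rate seen among those analyzed in an arm is

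[(1−f)·p + f·p·(1−d_b)] / [(1−f) + f·(p·(1−d_b) + (1−p)·(1−d_n))]

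The documents give none of f, d_b or d_n. Assumptions: d_n = 0.10; d_b = 0.40 or 0.60 in the affected arm and 0.10 in the other; 460 randomized per arm (920/2).

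Example with p = 0.06, f = 0.50, d_b = 0.60: numerator 0.03 + 0.012 = 0.042; denominator 0.5 + 0.5·(0.024 + 0.846) = 0.935; observed rate 4.49% against 6.00% in the other arm.

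No true effect, 6% in both arms (each pair is d_b = 0.40 / 0.60):

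| Route share f | Affected arm, observed | Spurious difference, points | Two-sided rejection at 5% |
|---|---|---|---|
| 10% | 5.83 / 5.71% | 0.17 / 0.29 | 5.1 / 5.4% |
| 25% | 5.56 / 5.27% | 0.44 / 0.73 | 5.9 / 7.6% |
| 50% | 5.10 / 4.49% | 0.90 / 1.51 | 8.9 / 16.9% |

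The difference goes against clipping if no-clip bleeders refuse more, and in its favor by the same amount if clip bleeders do. Rejection uses the normal approximation. At the final level of 0.044 (Section 3.2.10.3) it is 4.5–4.8% at a 10% share and 8.0–15.6% at 50%; the interim look is ignored in both.

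True rates 8% vs 3%, a 5-point difference:

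| Route share f | No-clip bleeders refuse more | Clip bleeders refuse more |
|---|---|---|
| 10% | 4.78 / 4.63 | 5.09 / 5.15 |
| 25% | 4.43 / 4.05 | 5.22 / 5.37 |
| 50% | 3.82 / 3.02 | 5.46 / 5.77 |

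**When there is no false signal.** If refusal is unrelated to outcome (10% in both arms), the type I error stays at 5.0%. It also stays at 5.0% if bleeders refuse more, but equally in both arms (40%). In that second case, at 8% vs 3% and a 25% share, power is 88.6%, compared with 91.5% when nobody is lost.

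**Sensitivity to a few patients.** With 37 vs 25 bleeds of 460 per arm, the uncorrected chi-square gives p = 0.115. If four clip-arm bleeders do not sign (21 of 456), p = 0.033, below 0.044. This illustrates fragility; it is not a forecast.

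**The case against.** The strongest case against is about size. The route is confined to some centers with few referrals, Section 7 puts large polyps at about 1–2% of colonoscopies, and the sample size section describes consent before treatment. All of this suggests a small share, where the bias is 0.2–0.3 points. The scenario also needs bleeders in one arm to refuse far more often than bleeders in the other, and it treats every bleed as preceding the decision. If only half do, the spurious difference falls to about 0.1 points at a 10% share and 0.2–0.4 at 25%; if a quarter do, it is 0.2–0.4 even at 50%. These points are sound and limit how much can be claimed. But the plan neither states nor caps the share, and nothing in it makes the decision precede a bleed.

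Two further points are partly right. Section 8.2 retains enrollment logs and, if applicable, a master randomization list, so counts by arm might be reconstructed later; that is not a planned report. And Section 3.2.10.1 does not itself say that non-signers are dropped. This is an inference, but enrollment only on consent, together with data only from participants, leaves no outcome data for them.

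The advance opt-out sheet acts before randomization, so it cannot prevent refusal after treatment. The practical argument in Section 7 justifies having the route, not the absence of safeguards.

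**Conclusion.** The concern holds and should be addressed. The structural gap is clear from the text: following the plan as written removes randomized non-signers, possibly after a bleed is known, from a comparison labeled intention-to-treat, and nothing planned would show how many left each arm. The size is uncertain. Under the assumed refusal rates, the effect is negligible at a 10% route share and becomes material only when the share is large, reaching 0.9–1.5 points at 50% against a design difference of 5 points. A false signal under no effect requires signing to depend on arm and outcome jointly, and it may go in either direction. All figures shrink if few bleeds precede the decision.

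**What to change.** 1. **Section 3.2.10.1.** Prespecify a sensitivity analysis of the primary comparison in patients who consented before the procedure, where this selection cannot arise. Show results by consent route descriptively only, because route is tied to lower-referral centers.
2. **Section 7.** Seek the decision at the 24–72 hour call already planned in Sections 3.2.9.3 and 3.3, with telephone consent documented. Reconcile this with the signature requirement in the same paragraph, and record whether any event preceded consent. A hard cut-off is not advised, because it would itself exclude randomized patients.
3. **Reporting.** From the randomization list and the enrollment logs in Section 8.2, report by arm the numbers randomized, consenting and not consenting on this route. Extend the Section 3.2.2 log to these patients and reconcile it with the data restriction in Section 3.3.2, as the IRB allows.

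The cost is one analysis, some wording, and minor logging that needs IRB agreement. The sensitivity analysis is less precise: at 8% vs 3%, with n = 460·(1−f) per arm, the 95% half-width 1.96·√[(0.08·0.92 + 0.03·0.97)/n] rises from 2.9 points to 3.1, 3.4 or 4.1 at route shares of 10%, 25% or 50%. It gives an estimate free of this selection but is a weak detector of it. The half-width of the full-minus-subset difference, √(subset² − full²), is about 1.0, 1.7 and 2.9 points at those shares, larger than the biases in the table. The counts by arm are therefore needed as well.
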